**Recurrence Intervals to Determine Whether an Infection is the Same or New:**

CMV, HSV, EBV, HHV6: 2 months (< 60 days)

VZV, HZV: 2 weeks (< 14 days)

Bacterial, non-Clostridium difficile: 1 week (< 7 days)

Bacterial, Clostridium difficile: 1 month (< 30 days)

Yeast: 2 weeks (< 14 days)

Molds: 3 months (< 90 days)

Helicobacter: 1 year (< 365 days)

Adenovirus, Enterovirus, Influenza, RSV, Parainfluenza, Rhinovirus: 2 weeks (< 14 days)

Polyomavirus (BK virus): 2 months (< 60 days)

For infections coded as “Disseminated,” any previous infection with the same organism but different site within the recurrence interval for that organism will be counted as part of the disseminated infection.

Reference:

Blood and Marrow Transplant Clinical Trials Network, Technical MOP, Version 3.0, 19 Mar 2013.  
Accessed from <http://www.bmtctn.net>. Accessed on 31 August 2015.

## 12.9 Appendix 9: Staging and Grading of Acute Graft versus Host Disease

### Staging of aGVHD

Skin†	0 = No rash 1 = Maculopapular rash < 25% of body surface 2 = Maculopapular rash 25%-50% of body surface 3 = Generalized erythroderma (maculopapular rash > 50%) 4 = Generalized erythroderma with bullous formation and desquamation
Lower Intestinal Tract‡	0 = Diarrhea < 500 mL/day or 280 mL/m  1 = Diarrhea > 500 but ≤ 1000 mL/day or 280-555 mL/m  2 = Diarrhea > 1000 but ≤ 1500 mL/day or 556-833 mL/m  3 = Diarrhea > 1500 mL/day or > 833mL/m  4 = Severe abdominal pain with or without ileus or stool with frank blood or melena
Upper Intestinal Tract§	0 = No protracted nausea and vomiting 1 = Persistent nausea, vomiting, or anorexia
Liver¶	0 = Bilirubin < 2.0 mg/dL 1 = Bilirubin 2.0 – 3.0 mg/dL 2 = Bilirubin 3.1 – 6.0 mg/dL 3 = Bilirubin 6.1 – 15.0 mg/dL 4 = Bilirubin > 15.0 mg/dL
Biopsy Result	PS = Positive NG = Negative EQ = Equivocal ND = Not done

†Use 'Rule of Nines' or burn chart to determine extent of rash.

‡Downgrade 1 stage if an additional cause of diarrhea has been documented.

§Persistent nausea with histologic evidence of GVHD in the stomach or duodenum.

¶Range given as total bilirubin. Downgrade 1 stage if an additional cause of elevated bilirubin has been documented.

### Overall Grade of aGVHD†

Grade 0: 
 
No skin rash and
 
No protracted nausea and vomiting and
 
No diarrhea or diarrhea < 500 mL/day and
 
Bilirubin < 2.0 mg/dL
 
	Grade III: 
 
Skin – no rash to rash > 50% of body surface with
 
Diarrhea >1500 mL/day or severe abdominal pain or
 
Bilirubin 3.1 – 15.0 mg/dL
 

Grade I: 
 
Skin Rash < 50% of body surface and
 
No diarrhea or diarrhea < 500 mL/day and
 
Bilirubin < 2.0 mg/dL
 
	Grade IV‡: 
 
Skin – generalized erythroderma or
 
Bilirubin > 15.0 mg/dL
 

Grade II: 
 
Skin rash > 50% of body surface or
 
Diarrhea > 500 mL/day or
 
Bilirubin 2.0 – 3.0 mg/dL or
 
Persistent nausea/vomiting
 
	

†Criteria for grading given as minimum degree of organ involvement required to confer that grade.

[figure not shown]
‡Grade IV may also include lesser organ involvement but with extreme decrease in performance status.

References:

BMT CTN 0201 Data listing for data review committee (DRC). Updated 12 Mar 2010.

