### 2.3.3 Exploratory Variables

- Clinical outcomes:
  - Overall mortality
  - Incidence of CMV EOD
  - Incidence of Grade 3-4 aGVHD
  - Incidence of severe cGVHD
  - Incidence of grade 3 treatment-emergent viral, bacterial, or fungal infections other than CMV
  - Maximum grade of aGVHD
  - Maximum cGVHD score
  - Relapse mortality (death due to relapse of the subject's primary disease)
  - Non-relapse mortality (death due to causes unrelated to the subject's primary disease)
  - Incidence of graft rejection
  - Incidence of failure to engraft
  - Time to engraftment
  - Time to platelet recovery
  - Incidence of relapse of primary disease requiring therapy.
  - Number of episodes of protocol-defined CMV viremia [CMV plasma viral load  $\geq 1000$  IU/mL by the Abbott RealTime CMV assay as assessed by the central laboratory]
  - Time to Grade 3 treatment-emergent viral, bacterial, or fungal infections other than CMV
- Duration of hospitalization(s)
- Health economic/resource utilization

- Subjects' quality of life (QOL) variables (EQ-5D, Functional Assessment of Cancer Therapy – Bone Marrow Transplant [FACT-BMT], and Work Productivity and Activity Impairment Questionnaire: General Health [WPAI: GH])
- Immunogenicity variables
  - T-cell responses to pp65
  - gB-specific antibody levels

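### Protocol Appendix 9 lets isolated stage 3 skin meet both Grade II and Grade IV, so the same subject can be in or out of grade 3-4 acute GVHD

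*Protocol*

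**What the plan says.** Protocol 5.3.2 makes the Appendix 9 tables the basis for the occurrence, stage and overall grade of acute GVHD.

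In the staging table, skin stage 3 is "3 = Generalized erythroderma (maculopapular rash > 50" (percent), and stage 4 is "4 = Generalized erythroderma with bullous formation and desquamation". Stage 3 thus carries two names for one finding, and blistering with desquamation is what separates stage 4 from it.

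The overall grade table does not use stage numbers. It has three relevant skin lines:

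- Grade II: "Skin rash > 50% of body surface or", one item in a list of alternatives.
- Grade III: "Skin – no rash to rash > 50% of body surface with", followed by gut or liver criteria.
- Grade IV: "Skin – generalized erythroderma or", followed by a bilirubin criterion.

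A footnote explains how to read the lines: "Criteria for grading given as minimum degree of organ involvement required to confer that grade". A second footnote allows Grade IV with lesser organ involvement when performance status has fallen extremely.

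Two outcomes use the result. Protocol 2.3.3 lists "Incidence of Grade 3-4 aGVHD" and the maximum grade as exploratory variables. Protocol 7.4.3 plans a CMH test for the first and a stratum-adjusted Kruskal-Wallis test for the second. SAP 6.1.3 keeps both as exploratory, and SAP 7.4.3.1 only summarizes them descriptively.

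**The concern.** The overall table describes skin in words that the staging table has already given to stage 3. If generalized erythroderma means what the staging table says, the Grade II and Grade IV skin lines name the same finding, and each is sufficient alone. Neither the protocol nor the SAP says which applies, and the SAP gives no rule for deriving overall grade from organ stages.

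At stake is whether a subject with rash over half the body surface and no qualifying gut or liver involvement counts as a grade 3-4 event. Acute GVHD is assessed weekly through day 100, and after that weekly until resolution once diagnosed. Approximately 90 sites are planned. Two sites could apply the appendix in good faith and record different grades for the same presentation. The sponsor has some interest in the outcome, since Protocol 1.3.2.2 cites a numerically lower phase 2 rate of grade 3-4 acute GVHD among the possible benefits of vaccination.

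**Working it through.** No planned sample size, power or error rate depends on this definition, so there is no figure of the plan to reproduce. The check sets the two tables side by side and then counts how far the ambiguity reaches.

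**Side by side**

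| Skin finding | Staging table | Overall grade table |
|---|---|---|
| Rash over 50%, described as rash | Stage 3 | Grade II alone; upper end of the Grade III range when gut or liver criteria are met |
| Rash over 50%, described as generalized erythroderma | Stage 3 | Grade IV alone |
| Generalized erythroderma with bullae and desquamation | Stage 4 | No line names the bullae or desquamation |

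The first two rows are one finding under the staging table and two different grades under the overall table.

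**How many stage combinations are affected**

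Inputs, all from Appendix 9: skin stages 0 to 4, lower gut 0 to 4, upper gut 0 to 1, liver 0 to 4. That gives 5 × 5 × 2 × 5 = 250 combinations. The overall table's volume and bilirubin limits match the organ stages as follows:

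- Grade II: lower gut stage 1 or more, upper gut stage 1, or liver stage 1.
- Grade III: lower gut stage 3 or 4, or liver stage 2 or 3.
- Grade IV: liver stage 4.

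The performance-status footnote is left out. The highest grade met is taken as the overall grade; this is my convention, as the appendix does not state one.

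Two readings of the Grade IV skin line are compared:

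- Literal: skin stage 3 or 4 qualifies.
- Narrow: only skin stage 4 qualifies.

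The readings can differ only at skin stage 3, which covers 5 × 2 × 5 = 50 combinations.

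1. Literal reading: all 50 are Grade IV.
2. Narrow reading: liver stage 4 still gives Grade IV, in 5 × 2 = 10 combinations. The other 50 − 10 = 40 change grade.
3. Of those 40, Grade III under the narrow reading has two sources. Liver stage 2 or 3 with any gut stage gives 2 × 5 × 2 = 20. Liver stage 0 or 1 with lower gut stage 3 or 4 gives 2 × 2 × 2 = 8. Together these are 28, which move between Grade III and Grade IV and stay inside grade 3-4.
4. The remaining 40 − 28 = 12 (liver 0 or 1, lower gut 0 to 2, upper gut 0 or 1: 2 × 3 × 2 = 12) are Grade II under the narrow reading and Grade IV under the literal one. These cross the endpoint boundary.

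A direct enumeration of all 250 combinations gives the same counts: 40 changes, of which 12 cross and 28 do not. The simplest crossing case is stage 3 skin with every other organ at stage 0.

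These are cells of a table, not patients. They show which subjects are exposed to the ambiguity, not how many there will be.

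**The case against.** The best answer is that the overall table makes sense under only one reading. If rash over 50% alone conferred Grade IV, the skin line of Grade II and the upper end of the Grade III skin range could never decide a grade. The other organ criterion for Grade IV, bilirubin above 15.0 mg/dL, is exactly liver stage 4, so skin stage 4 is the natural parallel. This stands as evidence of intent. It does not remove the conflict: the Grade IV line omits the features that define stage 4, the words it uses are defined as stage 3, and the footnote says each line is the minimum for its grade.

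It is also fair that the data may be recoverable. Protocol 5.3.2 calls for maximal grade and stage by key organ, so isolated stage 3 skin can be identified before unblinding. That stands, and it is why the remedy is cheap.

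A reader might go further and infer that the phase 2 contrast would be diluted. Protocol Table 3 gives 2 of 40 (5.0%) against 5 of 34 (14.7%), a ratio of 0.34. If an assumed 5% to 10% of each arm were added as extra events, the ratio would become 10.0/19.7 = 0.51 to 15.0/24.7 = 0.61. The documents do not support that inference:

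- They give no frequency of isolated stage 3 skin; the 5% to 10% is unanchored.
- Table 3 cites a 1974 grading paper, whereas Appendix 9 cites a 1995 consensus report and a trials-network data listing. How phase 2 graded this finding is unknown.
- The arithmetic assumes every such case is graded IV, whereas the ambiguity would more plausibly produce a mixture.
- The starting ratio rests on seven events, with P = 0.2364.

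Nor do the documents point to error that differs by arm: under Protocol 4.4.1 site staff are blinded, apart from the pharmacist and designated staff, including those who inject.

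**Conclusion.** Appendix 9 is inconsistent as written, and the point is minor. Isolated stage 3 skin meets the stated minimum for both Grade II and Grade IV, and no other text in the protocol or SAP resolves it. The ambiguity reaches 40 of 250 organ-stage combinations for overall grade and 12 of 250 for membership of grade 3-4, given the highest-grade convention and leaving aside the performance-status provision.

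Its reach is limited to two exploratory variables, for which the SAP plans no treatment comparison. The primary composite, the key secondary endpoints and the sample size do not depend on it. No effect on a rate or a treatment contrast can be quantified from the documents.

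A reader might also conclude that the documents establish stage 4 as the Grade IV skin criterion. They suggest it without stating it, and the grading sources they cite were not available for this review. The supportable conclusion is that the tables must be reconciled.

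**What to change.** 1. In Appendix 9, write each overall grade in the appendix's own organ stage numbers, so that each skin stage taken alone maps to one overall grade. The protocol's clinical authors should confirm the mapping against the sources they cite.
2. In the SAP, before unblinding, state that overall grade is derived by program from the organ stages recorded at each assessment, using that single mapping and taking the highest grade met, and that maximum grade and grade 3-4 status follow from it.
3. Keep the performance-status route to Grade IV. The footnote gives no threshold for it, so the SAP should say how such cases are recognized, for example by flagging site-recorded Grade IV that organ stages alone do not explain.
4. List every discordance between the derived and the site-recorded grade.

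The cost is a short appendix clarification, one derived variable and one listing. Organ stages are already recorded, so no new data collection is needed.

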## 12.10 Appendix 10: Rule of Nines Burn Chart

## **12.11 Appendix 11: Criteria for the Diagnosis of Chronic Graft Versus Host Disease**

The diagnosis of cGVHD requires the following 3 criteria:

1. Distinction from acute GVHD,
2. Presence of at least 1 diagnostic clinical sign of chronic GVHD or presence of at least 1 distinctive manifestation confirmed by pertinent biopsy or other relevant tests,
3. Exclusion of other possible diagnosis.

Organ or Site	Diagnostic (Sufficient to Establish the Diagnosis of cGVHD)	Distinctive (Seen in cGVHD, but Insufficient Alone to Establish a Diagnosis of cGVHD)	Other Features	Common (seen with Both Acute and Chronic GVHD)
Skin	Poikiloderma Lichen planus-like features Sclerotic features Morphea-like features Lichen sclerosus-like features	Depigmentation	Sweat impairment Ichthyosis Keratosis pilaris Hypopigmentation Hyperpigmentation	Erythema Maculopapular rash Pruritus
Nails		Dystrophy Longitudinal ridging, splitting, or brittle features Onycholysis Pterygium unguis Nail loss (usually symmetric; affects most nails)†		
Scalp and body hair		New onset of scarring or nonscarring Scalp alopecia (after recovery from chemoradiotherapy)  Scaling, papulosquamous lesions	Thinning scalp Hair, typically patchy, coarse, or dull (not explained by endocrine or other causes) Premature gray hair	
Mouth	Lichen-type features Hyperkeratotic plaques Restriction of mouth opening from sclerosis	Xerostomia Mucocele Mucosal atrophy  Pseudomembranes† Ulcers†		Gingivitis Mucositis Erythema  Pain
Eyes		New onset dry, gritty, or painful eyes‡ Cicatricial conjunctivitis Keratoconjunctivitis sicca‡ Confluent areas of punctate  Keratopathy	Photophobia Periorbital Hyperpigmentation Blepharitis (erythema of the eyelids with edema)	
Genitalia	Lichen planus-like features Vaginal scarring or stenosis	Erosions† Fissures† Ulcers†		

Table continued on next page

Organ or Site	Diagnostic (Sufficient to Establish the Diagnosis of cGVHD)	Distinctive (Seen in cGVHD, but Insufficient Alone to Establish a Diagnosis of cGVHD)	Other Features	Common (seen with Both Acute and Chronic GVHD)
Gastrointestinal Tract	Esophageal web Strictures or stenosis in the upper mid third of the esophagus†		Exocrine Pancreatic insufficiency	Anorexia Nausea  Vomiting Diarrhea Weight loss Failure to thrive (infants and children)
Liver				Total bilirubin, Alkaline phosphatase > 2 x ULN Alanine aminotransferase or aspartate aminotransferase >2 x ULN
Lung	Bronchiolitis obliterans diagnosed with lung biopsy	Bronchiolitis obliterans diagnosed with Pulmonary function test and radiology‡		Bronchiolitis obliterans organizing pneumonia
Muscles, fascia, joint	Fasciitis Joint stiffness or contractures secondary to sclerosis	Myositis or polymyositis‡	Edema Muscle cramps  Arthralgia or arthritis	
Hematopoietic and immune systems			Thrombocytopenia Eosinophilia Lymphopenia  Hypo- or Hyper $\gamma$ -globulinemia Autoantibodies (autoimmune hemolytic anemia and idiopathic thrombocytopenic purpura)	

Table continued on next page

Organ or Site	Diagnostic (Sufficient to Establish the Diagnosis of cGVHD)	Distinctive (Seen in cGVHD, but Insufficient Alone to Establish a Diagnosis of cGVHD)	Other Features	Common (seen with Both Acute and Chronic GVHD)
Other			Pericardial or Pleural effusions Ascites Peripheral neuropathy Nephrotic syndrome Myasthenia gravis Cardiac conduction abnormality or cardiomyopathy	

aGVHD: acute graft-versus-host disease; cGVHD: chronic graft-versus-host disease; GVHD: graft-versus-host disease; ULN: upper limit of normal

†In all cases, infection, drug effects, malignancy, or other causes must be excluded.

‡Diagnosis of chronic GVHD requires biopsy or radiology confirmation (or Schirmer test for eyes).

Note: Other features can be acknowledged as part of the chronic GVHD symptomatology if the diagnosis is confirmed.

Reference:

## **12.12 Appendix 12: Grading of Chronic Graft versus Host Disease**

### **Maximum grade of chronic GVHD**

Limited - localized skin involvement and/or hepatic dysfunction due to cGVHD.

Extensive - 1 or more of the following:

- Generalized skin involvement; or,
- Liver histology showing chronic aggressive hepatitis, bridging necrosis or cirrhosis; or,
- Involvement of the eye: Schirmer's test with < 5 mm wetting; or,
- Involvement of minor salivary glands or oral mucosa demonstrated on labial biopsy; or,
- Involvement of any other target organ.

## 12.13 Appendix 13: Organ Scoring and Global Scoring of Chronic Graft versus Host Disease

### Organ Scoring cGVHD

	SCORE 0	SCORE 1	SCORE 2	SCORE 3
PERFORMANCE SCORE:  KPS	 Asymptomatic and fully active ( KPS 100%)	 Symptomatic, fully ambulatory, restricted only in physically strenuous activity (KPS 80%-90%)	 Symptomatic, ambulatory, capable of self-care, >50% of waking hours out of bed (KPS 60%-70%)	 Symptomatic, limited self-care, >50% of waking hours in bed (KPS <60%)
SKIN Clinical features  Maculopapular rash  Lichen planus-like features  Papulosquamous lesions or ichthyosis  Hyperpigmentation  Hypopigmentation  Keratosis pilaris  Erythema  Erythroderma  Poikiloderma  Sclerotic features  Pruritus  Hair involvement  Nail involvement %BSA Involved 	 No symptoms	 18% BSA with disease signs but NO sclerotic features	 19%-50% BSA OR involvement with superficial sclerotic features “not hidebound” (able to pinch)	 50% BSA OR deep sclerotic features “hidebound” (unable to pinch) OR impaired mobility, ulceration or severe pruritus
MOUTH	 No symptoms	 Mild symptoms with disease signs but not limiting oral intake significantly	 Moderate symptoms with disease signs with partial limitation of oral intake	 Severe symptoms with disease signs on examination with major limitation of oral intake
EYES Mean tear test (mm):  >10  6-10  ≤ 5  Not done	 No symptoms	 Mild dry eye symptoms not affecting ADL (requiring eye drops ≤ 3 x per day) OR asymptomatic signs of keratoconjunctivitis sicca	 Moderate dry eye symptoms partially affecting ADL (requiring drops > 3 x per day or punctual plugs), WITHOUT vision impairment	 Severe dry eye symptoms significantly affecting ADL (special eyewear to relieve pain) OR unable to work because of ocular symptoms OR loss of visions caused by keratoconjunctivitis sicca
Table continued on next page				

	SCORE 0	SCORE 1	SCORE 2	SCORE 3
GI Tract	 No symptoms	 Symptoms such as dysphagia, anorexia, nausea, vomiting, abdominal pain or diarrhea without significant weight loss (<5%)	 Symptoms associated with mild to moderate weight loss (5%-15%)	 Symptoms associated with significant weight loss >15%, requires nutritional supplement for most calorie needs OR esophageal dilation
LIVER	 Normal LFT	 Elevated Bilirubin, AP*, AST or ALT < 2 x ULN	 Bilirubin > 3 mg/dL or Bilirubin, enzymes 2 x-5 x ULN	 Bilirubin or enzymes > 5 x ULN
LUNGS†  FEV1   DLCO 	 No symptoms   FEV1 > 80% OR LFS = 2	 Mild symptoms (shortness of breath after climbing 1 flight of steps)   FEV1 60%-79% OR LFS = 3-5	 Moderate symptoms (shortness of breath after walking on flat ground)   FEV1 40%-59% OR LFS = 6-9	 Severe symptoms (shortness of breath at rest; requiring O 2 )   FEV1 ≤ 39% OR LFS = 10-12
JOINTS AND FASCIA	 No symptoms	 Mild tightness of arms or legs, normal or mild decreased ROM AND not affecting ADL	 Tightness of arms or legs OR joint contractures, erythema thought due to fasciitis, moderate decrease ROM AND mild to moderate limitation of ADL	 Contractures WITH significant decrease of ROM AND significant limitation of ADL (unable to tie shoes, button shirts, dress self etc.)
GENITAL TRACT	 No symptoms	 Symptomatic with mild signs on exam AND no effect on coitus and minimal discomfort with gynecologic exam	 Symptomatic with moderate signs on exam AND with mild dyspareunia or discomfort with gynecologic exam	 Symptomatic WITH advanced signs (stricture, labial agglutination or severe ulceration) AND severe pain with coitus or inability to insert vaginal speculum
Other indicators, clinical manifestations or complications related to chronic GVHD (check all that apply and assign a score to its severity (0-3) base on its functional impact where applicable (none - 0, mild - 1, moderate -2, severe - 3)				
Esophageal stricture or web _____ Pericardial Effusion _____ Pleural Effusion(s) _____				
Ascites (serositis) _____ Nephrotic syndrome _____ Peripheral Neuropathy _____				
Myasthenia Gravis _____ Cardiomyopathy _____ Eosinophilia > 500/ μL _____				
Polymyositis _____ Cardiac conduction defects _____ Coronary artery involvement _____				
Platelets < 100,000/μL _____ Progressive onset _____				
OTHERS: Specify: _____				

ADL: activities of daily living; BSA: bovine serum albumin; cGVHD: chronic graft-versus-host disease; DLCO: diffusing lung capacity of carbon monoxide; FEV1: forced expiratory volume ; GVHD: graft-versus-host disease; KPS: Karnofsky Performance Scale ; LFS: lung function score; PFT: pulmonary function testing; ROM: range of motion

Footnotes continued on next page

Organ scoring of chronic GVHD. \*AP may be elevated in growing children, and not reflective of liver dysfunction. †Pulmonary scoring is to be performed using both the symptom and PFT scale whenever possible, if performed based on symptoms. When discrepancy exists between pulmonary symptom or PFT scores the higher value should be used for final scoring. Scoring using the LFS is preferred, but if DLCO is not available, grading using FEV1 should be used. The LFS is a global assessment of lung function after the diagnosis of bronchiolitis obliterans has already been established. The percent predicted FEV1 and DLCO (adjusted for hematocrit but not alveolar volume) should be converted to a numeric score as follows: >80% = 1; 70%-79% = 2; 60%-69% = 3; 50%-59% = 4; 40%-49% = 5; < 40% = 6. The LFS = FEV1 score + DLCO score, with a possible range of 2-12.

### **Global Scoring of cGVHD**

- Mild: 1 or 2 organs or sites (except lung), with no clinically significant functional impairment (maximum of score 1 in all affected organs or sites).
- Moderate:
  - At least 1 organ or site with clinically significant but no major disability (maximum score of 2 in any affected organ or site) or;
  - 3 or more organs or sites with no clinically significant functional impairment (maximum score of 1 in all affected organs or sites) or;
  - A lung score of 1
- Severe:
  - Major disability caused by chronic GVHD (score of 3 in any organ or site);
  - A lung score of 2 or greater

## 12.14 Appendix 14: EQ-5D Questionnaire

Note that the below is an example; patients will be provided with forms to be completed.

Under each heading, please tick the ONE box that best describes your health TODAY

